### **Missing LBD or maximum thickness values:**

If both the LBD and maximum thickness values at a visit are missing, the tumor response will be set to missing for that visit.

If 1 of the 2 measurements is missing, the tumor response will be determined by just considering criteria as applied to the non-missing measurement. (note: this rule does not apply to the Month 12 LOCF and Last Visit endpoints where an LOCF algorithm for both tumor thickness and LBD will be applied, as described below).

Additionally, the following LOCF algorithm for tumor thickness and LBD will be applied for tumor response relative the Month 12 LOCF and Last Visit endpoints only (i.e., this LOCF algorithm does not apply to the individual visits, only the Month 12 LOCF and Last Visit timepoints).

- If a subject is missing a tumor thickness and/or their LBD assessments as a scheduled visit, an LOCF approach will be used to impute the missing data from the previous visits (ie, an LOCF approach will be applied to the tumor thickness and separately an LOCF approach will be applied to the LBD). If a patient has no non-missing post-baseline visits, the baseline value will be used. The assessment of tumor response (i.e., as described above) will be applied using the LOCF'd tumor thickness and LBD values.

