## 4.8 Methods To Be Used For Handling Missing Data

When summarizing categorical variables, subjects with missing data are generally not included in the calculations of percentages unless otherwise specified. When needed, the category of "Missing" is created and the number of subjects with missing data is presented.

When summarizing continuous variables, subjects with missing data are not included in calculations. No imputations are made.

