#### 1. Based on maximum thickness and LBD and subject receiving Standard of Care

Tumor response (PR, SD, or DP) will be based on the algorithm as defined in Section 8.1.1, with the modification that Investigator determination mentioned in DP definition will not be considered and if a subject receives standard of care they will be considered as having met the disease progression (DP) criteria from the date standard of care was administered.

Note that for the Month 12 LOCF and Last Visit timepoints:

- If a patient receives standard of care prior to their Month 12 Visit, the subject will be considered as having met DP, even if the LBD and/or tumor thickness assessments are being LOCF'd from a time-point previous to the SOC being administered.
- Similarly, if a patient receives standard of care prior to their Last Visit, the subject will be considered as having met DP, even if the LBD and/or tumor thickness assessments are being LOCF'd from a time-point previous to the SOC being administered.

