#### 8.1.7 Tumor Reponse by B-scan Ultrasound and Largest Basal Diameter by Fundus Photography

Number and percentage of subjects with tumor control (PR and SD) on both tumor thickness and LBD and tumor progression on either tumor thickness or LBD in the study eye will be summarized at each visit by cohort, overall and for subgroups defined in Section 4.4. Definitions in Section 8.1 will be used.

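### In the by-visit response tables, one non-progressing measurement is enough to be scored as tumor control, although control is defined on both thickness and LBD

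*SAP*

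**What the plan says.** SAP Section 8.1.1 makes stable disease a joint condition: thickness change between -0.5 and +0.5 mm, and LBD change between -0.5 and +1.0 mm. Each route to partial response needs a reduction of more than 0.5 mm in one dimension and no progression in the other. Progression needs only one dimension beyond its limit. Section 8.1.7 carries this into the by-visit summaries, which count "tumor control (PR and SD) on both tumor thickness and LBD and tumor progression on either tumor thickness or LBD".

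The missing-value text in Section 8.1.1 then sets a different standard for individual visits: "If 1 of the 2 measurements is missing, the tumor response will be determined by just considering criteria as applied to the non-missing measurement". It limits its own reach: "this rule does not apply to the Month 12 LOCF and Last Visit endpoints", where each measurement is carried forward separately. If both measurements are absent, "the tumor response will be set to missing for that visit". The general convention in Section 4.8 is that "subjects with missing data are generally not included in the calculations of percentages unless otherwise specified".

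Separately, Section 8.1 Method 1, on which Methods 2 and 3 build, says that "if a subject receives standard of care they will be considered as having met the disease progression (DP) criteria from the date" of its administration.

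In the protocol (Sections 10.1.10, 10.3.4 and 10.3.7, and Appendix 1), fundus photographs are taken at Week 6 but no B-scan is scheduled. From Week 12 both are scheduled at every visit.

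**The concern.** A progression score based on one measurement is sound, because one dimension is enough. A control score based on one measurement is unverified, because the other dimension could have progressed. The missing-value rule treats the two alike. It can hide progression but cannot create it, and the tables still describe the result as control on both dimensions.

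This affects the by-visit response tables for all three methods in the ITT population (14.2.1.3.1 to .3) and in the Efficacy Evaluable population (14.2.3.3.1 to .3). The sensitivity analyses in SAP Section 8.3 vary the population and the use of data after standard of care, but never this rule, so no planned output would reveal its effect. The study tests no hypothesis. The descriptive percentages are the result, and their label should match what was measured.

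**Working it through.** The plan states no assumed control rate, missingness rate or sample size calculation, so there is no figure of its own to reproduce.

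**Classification check.** I applied the Section 8.1.1 limits under Method 1, with no standard of care and exactly one measurement missing:

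| Available measurement | Score under the rule | Score if the missing one had progressed |
|---|---|---|
| Reduced by more than 0.5 mm | PR | DP |
| Within the stable range | SD | DP |
| Beyond its progression limit | DP | DP |

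The same three rows apply whichever measurement is available, giving six cells. Four of the six are scored as control without the second test, and all four would be DP if the missing value had progressed. The two DP cells never change. Between control and progression the error therefore has one direction. Between PR and SD it does not: a lone stable value is scored SD even if the missing dimension had shrunk.

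**Size in a table (assumptions, not document figures).** Let p be the progression probability in each dimension, equal and independent. Let m be the share of subjects missing exactly one measurement, at random and split evenly.

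- True control = (1 - p)².
- Control under the rule = (1 - m)(1 - p)² + m(1 - p).
- Overstatement = m × p × (1 - p).

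Results:

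- p = 0.1, m = 0.05: 0.05 × 0.1 × 0.9 = 0.0045, or 0.45 points.
- p = 0.2, m = 0.2: true control 64.0%, under the rule 67.2%, overstatement 3.2 points.
- p = 0.3, m = 0.3: 0.3 × 0.3 × 0.7 = 0.063, or 6.3 points.

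The first and last are the extremes of the range considered.

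**Week 6.** With thickness absent for everyone, the reported figure is 1 - p against a true (1 - p)²: 90% against 81% at p = 0.1, 80% against 64% at p = 0.2, and 70% against 49% at p = 0.3.

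**One subject.** A single misclassified subject moves the control percentage by 1/3 = 33.3 points in a cohort of 3, by 1/15 = 6.7 points in Cohort 12 if it reaches 15, and by 1/60 = 1.7 points overall.

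**Bounds.** At p = 0.2 and m = 0.2, counting single-measurement non-progressors as not controlled gives 0.8 × 0.64 = 51.2%. Counting them as controlled gives the 67.2% above. The true 64.0% lies between.

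**The case against.** The strongest reply is that the rule is stated openly and Section 8.1.7 defers to the definitions in Section 8.1, so nothing is concealed. The overall summaries at Month 12 LOCF and Last Visit are exempt. The protocol starts efficacy assessment at Week 12, and both scans are scheduled from then on. Most of this stands. It limits the reach of the point but does not reconcile a one-measurement score with a two-measurement definition. Week 6 also remains exposed, because SAP Section 8 assesses efficacy at each visit without excluding it.

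A second reply is that the obvious remedy can distort more than the rule. Counting every single-measurement non-progressor as a failure gives 51.2% against a true 64.0% in the example, 12.8 points too low where the rule is 3.2 points too high. At Week 6 it would give 0%. This objection is right, and it is why the fix reports bounds.

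A reader might also infer that subjects who received standard of care and had no later scan vanish from the by-visit tables. If 3 of 15 Cohort 12 subjects did so, 12/12 = 100% would appear instead of 12/15 = 80%. The documents do not support that as the plan's intention. Method 1 makes standard of care DP from its date, without limiting this to particular time points; the later note about Month 12 and Last Visit deals with carried-forward values. The count of 3 is also hypothetical. What remains is that the both-missing rule names no exception, so the order of precedence at individual visits is not explicit. Nor does standard of care feed the one-measurement rule, since such a subject is already DP.

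**Conclusion.** The point holds for the by-visit response tables only. A subject with one measurement missing is scored as controlled when the other is not progressing, and the resulting error in the control rate runs one way. Under the stated assumptions it is 0.45 to 6.3 points per table. It would be smaller if the two dimensions of the same tumor tend to progress together. From Week 12 it depends on missingness that the documents do not report. At Week 6 it affects every subject shown, barring an unscheduled B-scan.

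Three stronger readings are not supported:

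- That any subject with a missing measurement is scored as controlled. A lone progressing measurement is still DP.
- That control rates are inflated by 9 to 16 points. That is p(1 - p) at p = 0.1 and 0.2 (0.1 × 0.9 and 0.2 × 0.8), which applies to each affected subject-visit and not to a table.
- That the figures carry over to Methods 2 and 3. There an Investigator answer of No can turn measured progression into SD, so the calculation describes Method 1 only, whereas Method 3 is the primary one for the report.

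The change is worth making because the bias is systematic, the cohorts are small and the remedy is cheap. The headline summaries do not depend on it.

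**What to change.** For individual visits, replace the one-measurement rule in SAP Section 8.1.1 along these lines:

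- With one measurement missing, score DP if the available one meets the DP limit. Otherwise show the subject in a separate row, *Not evaluable (one measurement only)*, not counted as PR or SD.
- Give the control percentage twice, once with these subjects counted as not controlled and once as controlled, and present the pair as bounds.
- Do not present the composite response at visits where no B-scan is scheduled, such as Week 6. The LBD summary in Section 8.1.6 already covers the data collected there.
- State that the standard-of-care DP rule in Section 8.1 Method 1 takes precedence over the set-to-missing rule at individual visits through Week 52, so that these subjects stay in the denominator as DP. The limit matters because the final analysis follows Week 52 (SAP Section 4.2). Carrying standard-of-care subjects into Weeks 78 and 104 while others never reach those visits would bias control downward.

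The cost is SAP wording, one table row and a second percentage, with no new data. The downside is that by-visit control becomes a range, whose lower bound can fall clearly below the current figure when many measurements are missing.

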#### **8.1.2 Investigator Determination of Progression**

The investigator determination of progression is based on the corresponding Investigator judgement of progression eCRF question:

*Did the subject meet the protocol defined disease progression criteria and not yet receive additional therapy with standard of care (plaque brachytherapy, proton beam radiotherapy or enucleation) or additional therapy with AU-011 since the previous visit? (Yes/No Response).*

If the Response to this eCRF question is "No" and the subject met the criteria for disease progression (DP) based on the maximum thickness and LBD criteria defined in Section 8.1.1, then the tumor response will be classified as Stable Disease (SD).

Note that if a subject has started standard of care, they will be considered as having met the disease progression (DP) criteria from the date standard of care was administered.

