### 8.1 Tumor Response

Three different methods of determining tumor response will be applied. The rationale for using these 3 methods is to describe the data taking into consideration various factors (ie, criteria as stated below) that could have impacted the determination of tumor response. The following four criteria will be considered for tumor response assessment:

- a) The maximum thickness and LBD as defined in Section 8.1.1
- b) The investigator determination of the subject meeting protocol defined disease progression criteria as defined in Section 8.1.2
- c) The subject having an AE of Pigmentary Changes as defined in Section 8.1.3.
- d) The subject receiving standard of care

The 3 different methods for determining tumor response are:

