### **Missing Investigator judgement of progression:**

If the subject is missing the Investigator judgement of progression for a visit, the values from the subject's next non-missing Investigator judgement of progression will be used. If the subject does not have a next non-missing assessment (i.e., there are no subsequent assessments or they are all missing), the determination of the tumor response category will be based on the LBD and maximum thickness criteria values only (i.e., without consideration of the Investigator judgement of progression).

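### After AU-011 retreatment, SAP 8.1.2 can turn progression that is still measured into stable disease: the eCRF item mixes progression with treatment, and the exception covers only standard of care

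*SAP*

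**What the plan says.** SAP 8.1 derives tumour response in three ways. Method 1 uses measured thickness, largest basal diameter (LBD) and receipt of standard of care; in it, "Investigator determination mentioned in DP definition will not be considered". Method 2 adds the Investigator judgement of 8.1.2. Method 3 adds both 8.1.2 and the pigmentary-change rule of 8.1.3, and is the primary method for the study report.

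The judgement is a single eCRF item. It asks whether the subject did "meet the protocol defined disease progression criteria and not yet receive additional therapy with standard of care" (the modalities follow in brackets), and continues "or additional therapy with AU-011 since the previous visit? (Yes/No Response". If the answer is No and the measurements meet the DP criteria, "then the tumor response will be classified as Stable Disease (SD". One exception follows: "if a subject has started standard of care, they will be considered as having met the disease progression (DP) criteria". If the judgement is missing, "the values from the subject's next non-missing Investigator judgement of progression will be used"; if there is no later answer, the measurements alone decide.

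SAP 8.1 describes this criterion as "The investigator determination of the subject meeting protocol defined disease progression criteria as defined in Section 8.1.2", with no mention of treatment. SAP 8.1.7 counts partial response and SD as tumour control. For Month 12 LOCF and Last Visit, standard of care gives DP "even if the LBD and/or tumor thickness assessments are being LOCF'd from a time-point previous to the SOC being administered". There is no matching rule for AU-011.

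Protocol 8.3.3 allows AU-011 retreatment after Week 12, including for subjects who meet the progression definition. It also allows standard of care, naming enucleation, for growth below that definition. SAP 8.1.4 identifies standard of care from three coded terms: radiotherapy to the eye, brachytherapy to the eye and photodynamic therapy.

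**The concern.** The item asks two things at once: has the tumour progressed, and is the subject still untreated. A No can therefore mean either that the Investigator does not accept progression or that the subject was treated. The SAP reads every No as the first. It repairs the second meaning for standard of care but not for AU-011, although the item names both.

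Protocol 10.3.4 and 10.3.7 let the Investigator discount growth only for inflammation/swelling, hemorrhage or, for LBD, pigmentary change. Having been retreated is not among those reasons. At stake is the table that describes efficacy in the study report: a subject already accepted as progressed, retreated with AU-011 and still above the thresholds could be shown as tumour control, while the same subject given standard of care would be DP.

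**Working it through.** There is no plan figure to reproduce; the check is one of logic.

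**Inputs.** DP thresholds: more than 0.5 mm in thickness or more than 1.0 mm in LBD above baseline (SAP 8.1.1). Baseline is the last assessment on or before study day 1 and is not reset at retreatment (SAP 4.6). Scheduled efficacy visits: Weeks 12, 26, 39, 52, 78 and 104 (protocol 10.5). Retreatment visits: 24 hours after each administration, then 2, 4, 12 and 26 weeks after the course (protocol Appendix 4). Planned sizes: up to 12 in Cohort 9, 8 escalation cohorts of 3, about 60 overall.

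**Step 1, the item.** Yes = criteria met AND not treated. So No = criteria not met OR treated. Of the 4 combinations (criteria met or not, AU-011 since the last visit or not), 1 gives Yes and 3 give No. One of those 3 is a true progressor who was retreated.

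**Step 2, the methods.** Take a visit with AU-011 given since the previous one and progression still measured (illustrative sizes). Method 3 is shown on two readings: broad (all of 8.1.2 plus 8.1.3) and narrow (the No acts only through 8.1.3).

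| Measured change | Method 1 | Method 2 | Method 3, broad | Method 3, narrow |
|---|---|---|---|---|
| Thickness +0.7 mm | DP | SD | SD | DP |
| LBD only +1.4 mm, no pigmentary AE | DP | SD | SD | DP |
| LBD only +1.4 mm, pigmentary AE | DP | SD | SD | SD |
| Any of these, standard of care given | DP | DP | DP | DP |

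The broad reading has better support: Method 3 is said to add both sections and cites protocol 10.3.7, the thickness criterion, whereas 8.1.3 covers LBD-only progression.

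**Step 3, the visits.** Every literal reading gives No when AU-011 was given since the last visit at which the item was asked. After that they part:

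- Item also asked at the Appendix 4 visits, and the time qualifier limits the therapy clause: the No falls on those visits, and Weeks 26 to 104 may not be affected at all.
- Item asked only at scheduled visits, same reading of the qualifier: the first scheduled visit after retreatment is affected, normally 1 of the 5 after Week 12 (26, 39, 52, 78, 104) per course.
- Treatment clause read as ever treated: all later visits are affected.

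The documents do not say where the item is collected.

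**Step 4, missing answers and summary endpoints.** A missing judgement at a visit before retreatment takes the next available answer, which may be a No given after retreatment. Month 12 LOCF can fall after retreatment, because retreatment is allowed after Week 12. Last Visit can too: Appendix 4 records a late 26-week post-retreatment visit as Week 104. The SAP does not say which judgement goes with carried-forward measurements.

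**Step 5, size.** Shift per affected subject = 100/N points: 100/12 = 8.3 (Cohort 9); 100/24 = 4.2 (8 × 3, no cohort expanded); 100/60 = 1.7 (overall); 100/3 = 33.3 (one unexpanded escalation cohort).

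**Step 6, enucleation.** The 8.1.2 item and protocol 8.3.3 name it; the 8.1.4 terms do not. If a subject is enucleated for growth below the thresholds, the last measurements are within the SD range. If the coded terms miss the procedure, those values are carried forward and the subject is SD rather than DP.

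**The case against.** The strongest objection concerns exposure. A reader might infer that retreated progressors are shown as stable at every later scheduled visit, or that the first one is certainly affected. The documents support neither. If the item was asked at the Appendix 4 visits, the No may fall on a 24-hour visit, which has no B-scan, and a later scheduled visit would be Yes on one literal reading. This objection stands, and it leaves the set of exposed visits open.

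Sites may also have answered on progression alone, as SAP 8.1 describes the criterion. Nothing would then be misclassified. No completion guidance is available to settle this.

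On Method 3, the broad reading leaves 8.1.3 with almost nothing to do, and Methods 2 and 3 nearly coincide although three methods are announced. That is a fair argument for the narrow reading. It shows that the text needs settling and leaves Method 2 exposed either way.

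The study is descriptive, and Method 1, the raw measurements and the additional therapies (SAP 9.6.7, Listing 16.3.11) are all reported, so a careful reader could find the discordant cases. But Method 1 also drops legitimate Investigator discounting, and the sensitivity analyses in 8.3 remove only data after standard of care, so no planned table isolates the effect.

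The back-fill case is uncommon: retreatment needs Sponsor approval, and progression must be recorded on the eCRF (protocol 8.3.3). The 8.1.4 list may simply reflect the procedures coded so far, and nothing shows that an enucleation occurred. Both remain gaps in the rules that cost little to close.

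**Conclusion.** The rule is wrong as written, but its reach is limited. Taken literally, 8.1.2 changes progression that is still measured to SD when AU-011 was given since the item was last asked, and its exception covers only standard of care. Method 1 is not affected and Method 2 is. Method 3 is affected for thickness and LBD on the better-supported reading, and otherwise only for LBD-only progression with a pigmentary-change AE.

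The conclusion rests on sites having answered the item literally and on progression still being measured after retreatment. The number of subjects is unknown; each moves a rate by 100/N points.

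Three wider inferences are not supported. Planned Cycle 2 in Cohorts 10 to 12 is named apart from additional therapy, so it cannot be assumed to trigger a No. A visit before retreatment that was answered Yes keeps its DP. No net bias across all the response rules can be claimed.

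**What to change.** 1. In Methods 2 and 3, where progression was accepted before AU-011 retreatment (a Yes, or progression recorded on the eCRF), do not let a No that the AU-011 clause can explain change measured DP to SD by itself. Classify on the measurements, as 8.1.2 already does when no judgement exists. A tumour measuring below the thresholds keeps its measured category; permanent DP from retreatment is not needed. Keep the Investigator's discounting where existing records, such as AE records or a data query, show inflammation/swelling, hemorrhage or, for LBD, pigmentary change. The documents show only a Yes/No field, so do not assume that a cause-of-growth field exists. Where the cause cannot be established, flag the subjects and show the table both ways. State whether Method 3 applies all of 8.1.2 or only 8.1.3.

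2. Do not fill a missing judgement from a visit after AU-011 retreatment. Use the measurements alone, including at Month 12 LOCF and Last Visit.

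3. Add enucleation to the 8.1.4 terms.

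The cost is SAP wording, limited reprogramming and some record review or queries. Tumour control in Methods 2 and 3 may be slightly lower, and some inflammatory growth after retreatment may count as DP where its cause was not documented. SAP v5.0 already follows the first database lock of 25 Aug. 2021, so the change must be documented as made after that lock.
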